Statistical Analysis Plan (SAP)

Principal Investigator	[name] Professor of Gerontology, Psychology and Biomedical Engineering University of Southern California Los Angeles, California, USA
Protocol identification number	UP-17-00219
ClinicalTrials.gov identifier	NCT03458910
Author	[name] Research Associate [name] of Southern California Los Angeles, California, USA
Version	Draft 0.2
Date	09/09/2024

1. Objectives and hypotheses

The main objective of the study was to test the hypothesis that daily biofeedback sessions stimulating heart rate oscillatory activity in baroreflex frequencies affect the function of brain networks involved in emotion regulation. Our main outcome measure was pre-to-post intervention changes in resting-state right amygdala functional connectivity with a medial prefrontal cortex region associated with heart rate variability (HRV). Our secondary outcome measures were pre-to-post intervention changes in up- and down-regulation of amygdala activity and self-reported emotion regulation effectiveness during viewing emotional pictures, as well as changes in ratings of emotional well-being. Other secondary outcome measures included HRV during rest, measures of cerebral blood flow, decision making, stress responsivity and cognitive performance. As a post-hoc outcome measure, we examined pre-to-post intervention changes in resting-state left amygdala functional connectivity with a medial prefrontal cortex region.

2. Sample Size & Power consideration

121 younger adults and 72 older adults participated in the study.

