No prior studies had examined effects of these interventions on brain function so we were unable to estimate effect sizes based on prior neuroimaging data. We elected to power our study to detect medium or larger effect sizes. Our main planned statistical comparisons were repeated-measures ANOVAs with within-between interactions. For these, a total sample size of 46 would give 90% power to detect moderate effect sizes of $f=.25$ with $\alpha = .05$, given an assumed correlation among the repeated measures of .5 (Faul et al., 2007). We also planned to examine within-subject change within each of the conditions. A sample size of 44 in each condition (HRV-increase, HRV-decrease) would give 90% power to detect within-group change effect sizes of $d=.5$ in a two-tailed t-test with $\alpha = .05$ (Faul et al., 2007). Thus, we aimed for an N=200 completion rate across the two conditions and two age groups to be able to accommodate potential exclusions for movement during imaging or other data quality issues. Due to the COVID-19 pandemic leading to increased risk for participants completing lab visits, we terminated the study before achieving our initial goal of recruiting 100 older participants.

3. Outcomes

For most outcome measures, we examined group difference (HRV-increase vs. HRV-decrease) in pre-post intervention change. The average time between pre and post intervention assessment was 5 weeks.

Primary outcome measures

- Group difference in pre-post intervention change in resting state functional connectivity between the right amygdala and medial prefrontal cortex (mPFC)

Secondary outcome measures

- Group difference in pre-post intervention change in:
 - Emotion regulation ability measured by self-reported effectiveness when instructed to regulate emotion during viewing emotional pictures
 - The ability to up- and down-regulate amygdala activity when instructed to regulate emotion during viewing emotional pictures
 - Emotional well-being measured by the Profile of Mood States (POMS), the State Anxiety Inventory (SAI), the Trait Anxiety Inventory (TAI) and the Center for Epidemiologic Studies (CES-D)
 - HRV measured by high frequency power (HF)
 - HRV measured by low frequency power (LF)

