 - HRV measured by the root mean square of successive differences (RMSSD)
 - Inflammatory markers including C-reactive protein, IL-1b, IL-6, IL-8 and TNF-a
 - Stress recovery
 - Stress reactivity
- Group difference in cerebral blood flow during pre-intervention resting state and post-intervention paced-breathing
- Group difference in decision-making ability measured by multiple-choice responses during a computer-based decision-making task at the post-intervention MRI
- Group difference in the ability to up- and down-regulate task-relevant brain regions during a computer-based decision-making task at the post-intervention MRI

Other outcome measures

- Group difference in pre-post intervention change in:
 - Working memory measured by NIH Toolbox List Sorting Working Memory Test (LSWM)
 - Processing speed measured by NIH Toolbox Pattern Comparison Processing Speed Test (PCPS)
 - Inhibitory control and attention measured by NIH Toolbox Flanker Inhibitory Control and Attention Test (Flanker)
 - Sustained attention measured by Sustained Attention to Response Test (SART)
 - Stress measured by cortisol levels
- Group difference in recognition memory after about three and half weeks of training
- Group difference in recall memory after about three and half weeks of training

Safety outcomes

No adverse events were observed.

4. Populations and subgroups to be analyzed

Population analyzed is composed by all randomization subjects who completed assessments and whose data quality was sufficient for data analysis.

5. Analyses

Primary outcome measures

- Resting state functional connectivity between the right amygdala and medial prefrontal cortex (mPFC): We performed a 2 (time point: pre, post) \times 2 (condition: HRV-increase, HRV-decrease) mixed ANOVA. The effect of interest was a time \times condition interaction, and P values less than 0.05 were considered statistically significant.

Secondary outcome measures

- Emotion regulation (behavioral analysis):

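### Does the SAP's power statement for moderate effects leave the time-by-condition tests underpowered?

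*SAP*

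**What the plan says.** SAP Section 2 sets the aim in general terms: "We elected to power our study to detect medium or larger effect sizes". For the within-between interaction it states that "a total sample size of 46 would give 90% power to detect moderate effect sizes", with f=.25, alpha .05 and a correlation of .5 between the repeated measures. It adds a second purpose, "We also planned to examine within-subject change within each of the conditions", and a second calculation: "A sample size of 44 in each condition (HRV-increase, HRV-decrease) would give 90% power to detect within-group change effect sizes" of d=.5.

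The recruitment target is far larger than either figure: "we aimed for an N=200 completion rate across the two conditions and two age groups", to leave room for exclusions. The section then reports the shortfall and its cause, the pandemic: "we terminated the study before achieving our initial goal of recruiting 100 older participants". Attendance is given as "121 younger adults and 72 older adults participated in the study".

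Section 4 limits analysis to "all randomization subjects who completed assessments and whose data quality was sufficient for data analysis". In Section 5 the primary connectivity test is a 2 x 2 time-by-condition ANOVA with no age split stated. The inflammatory markers get the same 2 x 2 model, fitted to each age group on its own.

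**The concern.** A reader who sees 90% power for a moderate effect may assume that moderate means about half a standard deviation, since d=.5 appears two sentences later. For the interaction it does not: f=.25 there is a full standard deviation of difference in change. Two effects that differ twofold therefore sit under one stated aim, and the section does not say so.

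The tests most exposed are those fitted by age group. The older group ended at 72 instead of 100, and Section 2 does not restate power. A non-significant marker result in older adults could be taken as evidence of no effect when the test was simply insensitive. The Protocol (Research Objectives) predicts smaller improvements in older adults, so a null in that group beside a positive result in younger adults could be misread as an age effect.

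The 44 per condition adds a further doubt. If it was meant within each age group, 2 x 44 = 88 older adults were needed and 72 took part.

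**Working it through.** **Inputs.** From SAP Section 2: alpha .05, f=.25, correlation ρ=.5, N=46; d=.5 with 44 per condition; target 200; 121 younger and 72 older, so 121 + 72 = 193. Assumed: equal arms (the ratio is not stated) and everyone analysable, unless noted.

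**Reproducing the plan's figures.** For m=2 time points and two groups, λ = f²·N·m/(1−ρ), with F on (1, N−2) degrees of freedom.
- N=46: λ = 0.0625 × 46 × 2/0.5 = 11.5, power 91.2%.
- N=44: λ = 11.0, power 89.97%. So 46 is the smallest even total that reaches 90%.
- Paired t-test, n=44, d=.5: power 90.0%.

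Both stated sizes are correct.

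**What f=.25 means.** The interaction F equals a two-sample t-test on change scores, for which λ = (N/4)·d². Setting 11.5 = (46/4)·d² gives d = 1.0. At ρ=.5 the SD of change, σ√(2(1−ρ)), equals the raw SD, so this is 1.0 SD on either scale.

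**Power at other sizes.** A 0.5 SD difference corresponds to f=.125.

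| N | Power at 0.5 SD | Difference detectable with 90% power |
|---|---|---|
| 46 | 38% | 0.98 SD |
| 72 (older) | 55% | 0.77 SD |
| 100 (planned older) | 70% | 0.65 SD |
| 121 (younger) | 78% | 0.59 SD |
| 193 (pooled) | 93% | 0.47 SD |
| 200 (target) | 94% | 0.46 SD |

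For 90% power at 0.5 SD the total needed is 172 (90.3%; 170 gives 89.99%). At the SAP's own f=.25, 72 participants give λ = 0.0625 × 72 × 2/0.5 = 18 and power 98.7%.

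**Sensitivity.**
- Assumed exclusions of 10% and 20% bring power at 0.5 SD to 91% and 87% pooled, 73% and 68% in younger adults, and 51% and 46% in older adults.
- If 0.5 is counted in raw SD, power for younger and older adults is 64% and 42% at ρ=.3, and 94% and 77% at ρ=.7. The SAP gives no marker-specific correlation.
- Uneven arms matter little: 32/40 in older adults gives 54.8%.

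**Precision.** The expected 95% half-width is t(.975, N−2)·√(4/N): 0.47 SD at 72, 0.36 SD at 121 and 0.28 SD at 193. Observed differences of 0.03 to 0.47 SD in older adults would be non-significant yet compatible with 0.5 SD. The same holds for 0.14 to 0.36 SD in younger adults and 0.22 to 0.28 SD in the pooled sample.

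**The 44 per condition.** If pooled (about 96 per condition), power at d=.5 is 99.8%. If per age group, the smaller older-adult condition has at most 36 people and 83% power.

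**The case for a change.** The best case for a change is that the correction is cheap and the document is still marked as a draft. The inflammatory markers are listed secondary outcomes, Section 5 judges them by p<0.05 with no interval, and the only interaction power in view is 90% for a moderate effect. A few sentences and ten intervals (5 markers x 2 age groups) would guard against over-reading a null in older adults.

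Part of this stands. The SAP does not translate f=.25 into a difference in change, the marker tests in older adults are insensitive to 0.5 SD, and intervals would be more informative than p-values alone.

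It falls short of a defect for three reasons. First, 0.5 SD as a target for the interaction is brought in from outside: Section 2 uses d=.5 for change within one condition, which is a different quantity. Second, Section 2 attaches its 90% to the main planned comparisons and claims no power for secondary tests within an age group. Low sensitivity there contradicts nothing. Third, the warning about non-significant results is generic, since it applies to the pooled sample too over a narrower range. The insensitivity is also shown only for the 2 x 2 marker tests. It has not been calculated for the age-separate three-way ANOVAs, and it does not carry over to recall memory, which has no pre-post change.

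**Conclusion.** No change to the plan is needed. The sample-size figures are arithmetically right, and the plan misses no interaction power that it states. The design size was 200, not 46. With the 193 enrolled, the primary test has 93% power even on the stricter 0.5 SD reading, or 91% to 87% with 10% to 20% exclusions. This rests on the primary analysis pooling both age groups (Section 5 states no split), equal arms, and 0.5 counted in SD of change.

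The loss of sensitivity is real for the age-separate marker tests: the difference detectable with 90% power is 0.59 SD in younger and 0.77 SD in older adults, before exclusions. That follows from splitting the sample and stopping recruitment early, and Section 2 gives the group sizes, the missed goal and the reason. Enrolment is over, so restated power would change no decision. Whether 44 was meant pooled or per age group is an open detail: pooled there is no shortfall, and per age group power is at most 83% in the smaller older-adult condition. Analysts can report differences with 95% intervals, and explain the 1.0 SD equivalence, without altering the plan.

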To test whether stress reactivity changed during the course of the study and whether this depended on training condition, we performed a series of two-way mixed ANOVAs, one for each measure of stress reactivity. In these ANOVAs, time was a within-subjects factor (2 levels: pre- and post-intervention) and condition was a between-subjects factor (2 levels: HRV-Increase, HRV-Decrease). For each ANOVA, the effect of interest was a time x condition interaction, and only data from participants with values for both time points were included. P values less than 0.05 were considered statistically significant. ANOVAs were performed with R (Version 4.0.3) and the R package 'ez'.
- Cerebral blood flow measured by Arterial Spin Labeling (ASL):

We conducted a two-way ANOVA to examine whether whole-brain cerebral blood flow, as measured by arterial spin labeling MRI, changed over the course of the study as a result of training condition. Specifically, we examined cerebral blood flow at rest at the beginning of the study (i.e., before any intervention) and we examined cerebral blood flow during paced breathing at study completion (i.e., at the end of 5-week training). A 2x2 ANOVA was modeled with time as a within-subjects factor (2 levels: pre- and post-intervention) and training condition as a between-subjects factor (2 levels: HRV-Increase, HRV-Decrease). The effect of interest was the time x training condition interaction. Only participants with usable arterial spin labeling MRI scans at both time points were included in analyses. P values less than 0.05 were considered statistically significant. Statistical analyses were performed in IBM SPSS Statistics version 27.

- Decision-making (behavioral analysis):
To compare the response to unfair and fair offers between groups, we conducted two Mann-Whitney tests. In these analyses, acceptance rates for unfair and fair offers were dependent variables and group (HRV-Increase vs. HRV-Decrease) was defined as between subject independent variable. P values less than 0.05 were considered statistically significant.
- Decision-making (MRI analysis):

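### Cerebral blood flow is scanned at rest before training and during paced breathing after it, so the planned interaction cannot show whether flow changed over the study

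*SAP*

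**What the plan says.** SAP section 3 lists the outcome among the secondary measures as "Group difference in cerebral blood flow during pre-intervention resting state and post-intervention paced-breathing".

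SAP section 5, in the entry on arterial spin labelling (ASL), gives the aim as finding out whether whole-brain flow "changed over the course of the study as a result of training condition". It then describes the two measurements: "Specifically, we examined cerebral blood flow at rest at the beginning of the study", and "we examined cerebral blood flow during paced breathing at study completion". These are the two levels of a single within-subject factor called time, labelled only as before and after the intervention, in a 2 x 2 mixed ANOVA with training condition as the between-subject factor. "The effect of interest was the time x training condition interaction", tested at 0.05. "Only participants with usable arterial spin labeling MRI scans at both time points were included in analyses". The number of such participants is not given.

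The protocol (Week 7) lists paced breathing as an extra scan at that visit, with 10 seconds per breath as the example pace. It describes no paced-breathing scan at Week 2. Neither document describes an analysis of resting flow after training.

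**The concern.** Time point and breathing state move together without exception, so the model cannot tell a change over five weeks from a response to pacing on the day of the scan. The same holds for the effect of interest: time by condition is also state by condition.

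This would do no harm if both arms responded equally to pacing, but the protocol gives reason to doubt that. The increase-HRV arm is trained at about 6 breaths per minute and practises at home twice a day. The decrease-HR/HRV arm is asked to breathe normally. The example scan pace is 60/10 = 6 breaths per minute, so the final scan resembles the trained exercise of one arm only.

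Two misreadings are possible. A significant interaction could be reported as flow having changed over the study when only the response to pacing differs. A null interaction could be reported as no change when resting change and pacing response offset each other.

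**Working it through.** **The plan's own figures.** The SAP gives no power for blood flow. Its general statement for this type of test is that "a total sample size of 46 would give 90% power" at f = .25, alpha .05 and correlation .5 between repeated measures.
- Noncentrality = N f² m/(1 − ρ) = 46 × 0.0625 × 2/0.5 = 11.5, with 1 and 44 degrees of freedom. Power is 0.912. N = 44 gives 0.8997, so 46 is the smallest even total that reaches 90%.
- The within-condition figure of 44 per condition at d = .5 gives 0.900.

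Both reproduce.

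**What the interaction estimates.** Write R0 for Week 2 resting flow, R1 for Week 7 resting flow and P1 for Week 7 paced-breathing flow. For each participant

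P1 − R0 = (R1 − R0) + (P1 − R1).

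Taking arm differences, interaction = (arm difference in resting change) + (arm difference in pacing response). Only P1 and R0 enter the planned model.

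**Can the two parts be separated?** Take the cell-mean design with six columns: intercept, condition, time, state, condition x time and condition x state.
- As planned, its rank is 4 of 6 and time correlates 1.0 with state.
- With a Week 7 resting scan added in both arms, its rank is 6 of 6 and every term can be estimated.

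**If only the pacing response differs.** In a 2 x 2 mixed ANOVA the interaction F is the square of the two-sample t on change. With no arm difference in resting change and an arm difference d in pacing response (in SD of change, assumed), the noncentrality of t is d√(n/2). For example, at n = 44 per arm and d = .5 it is 0.5 × √22 = 2.35. Chance of a significant interaction, two-sided .05:

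| Per arm | d = .2 | d = .5 | d = .8 |
|---|---|---|---|
| 23 (the SAP's total of 46) | 10% | 38% | 76% |
| 44 (the SAP's per-condition figure) | 15% | 64% | 96% |
| 96 (121 + 72 = 193 participants, all usable: an upper bound) | 28% | 93% | over 99% |

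The SAP's f = .25 at correlation .5 is a difference of 1 SD of change (11.5 = d² × 23/2 gives d = 1), which is why the 23-per-arm row lies below 90%.

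**Different mixes of the two parts.** Simulation of 20,000 trials at 44 per arm, all correlations .5, equal variances, and a state shift of .5 SD common to both arms. Proportion significant:

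| Resting change | Pacing response | Planned interaction | Week 2 rest vs Week 7 rest | Week 7 rest vs Week 7 paced |
|---|---|---|---|---|
| 0 | 0 | 5% | 5% | 5% |
| 0 | .5 | 64% | 5% | 64% |
| .5 | 0 | 64% | 64% | 5% |
| .25 | .25 | 64% | 22% | 22% |
| .5 | −.5 | 5% | 64% | 64% |

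Three different mixes give the same result for the interaction, and an offsetting pair looks like no effect at all.

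**Time main effect.** With a common state shift of .5 SD and no change in resting flow in either arm, the time main effect is significant in 91% of trials at 23 per arm and 99.7% at 44 per arm. The interaction stays at about 5%.

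**The case against.** The strongest reply is that nothing is hidden and nothing is invalid. Section 3 keeps this outcome out of its list of ordinary pre-to-post changes and gives it a line of its own naming both states. In section 5 the loose opening phrase is followed at once by what was measured and when. Baseline precedes any intervention, so under randomisation the interaction is a coherent comparison of paced-breathing flow after training, referenced to resting flow before it. A trained response to pacing is itself an effect of training condition. The percentages above are ordinary power at assumed effects: they count detections of a real arm difference, not false positives for the planned contrast.

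Most of this stands. The planned test is sound for that composite, a common state effect cancels, and the section 3 line describes the measurement correctly. What does not follow is that naming the states supports the conclusion drawn from them. The aim in section 5 is worded much as it is for well-being, HRV, stress and cognition, where no difference in state between assessments is described, and a reader would take it the same way here. No model term, sensitivity analysis or limit on interpretation deals with the difference in state. Section 2 also says that change within each condition was to be examined. For this outcome such a change mixes time with state even when the arms respond equally to pacing.

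**Conclusion.** The concern holds. The confounding is exact and follows from the design, so it needs no assumption: the interaction gives the sum of resting change and pacing response and cannot apportion it. How far this could mislead does rest on assumptions, because the documents give neither component, the SD of change, nor the number of usable scan pairs. Over assumed pacing differences of .2 to .8 SD with resting flow unaffected, a significant interaction occurs in 15% to 96% of trials at 44 per arm. If the arms respond equally to pacing, the interaction keeps its 5% error rate when resting flow is unaffected.

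This is one secondary outcome, and the test, alpha and sample size are unaffected. The stated question should still be corrected, because following the plan exactly would support a conclusion that the contrast cannot give.

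**What to change.** 1. In the ASL entry of SAP section 5, replace the stated aim with: *the between-arm difference in post-training paced-breathing flow relative to pre-training resting flow*. Label the two levels of the time factor with their breathing states. State that, for this outcome, the time main effect and any within-arm change are not interpreted as training effects.
2. If a usable Week 7 resting ASL scan exists, add Week 2 rest versus Week 7 rest by condition as the test of change in resting flow, and report Week 7 rest versus Week 7 paced breathing by condition beside it. In the same participants the two estimates sum to the planned interaction. If no such scan exists, say that change in resting flow was not assessed.
3. Keep the planned interaction as it is.

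The cost is wording, plus at most two analyses of data already collected. The SAP is marked as a draft, so the change is practical. There are three drawbacks:
- The claim for this outcome becomes narrower.
- The SAP is written in the past tense, so the added comparisons must be labelled post hoc and must not replace the planned test.
- Step 2 may not be possible. The protocol describes resting scans at Week 2 and a repeat of the Week 2 assessments at Week 7, but does not confirm that resting ASL was among them.

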We conducted a three-way ANOVA to examine whether emotional intensity rated by participants during emotion regulation changed after HRV biofeedback intervention for younger and older adults separately. The 2 \times 2 \times 3 ANOVA model included three factors: time-point (2 levels: pre- and post-intervention), intervention condition (2 levels: HRV-Increase, HRV-Decrease) and regulation type (3 levels: down-regulation, viewing and up-regulation). P values less than 0.05 were considered statistically significant.
- Emotion regulation (MRI analysis):
We conducted a three-way ANOVA to examine whether BOLD activity in the left and right amygdala changed during emotion regulation after HRV biofeedback intervention for younger and older adults. The 2 \times 2 \times 3 ANOVA model for each amygdala included three factors: time-point (2 levels: pre- and post-intervention), intervention condition (2 levels: HRV-Increase, HRV-Decrease) and regulation type (3 levels: down-regulation, viewing and up-regulation). P values less than 0.05 were considered statistically significant.
- Emotional well-being (pre/post):
To test whether emotional well-being changed during the course of the study and whether this depended on training condition, we performed a series of two-way mixed ANOVAs, one for each measure. In these ANOVAs, time was a within-subjects factor (2 levels: pre- and post-intervention) and condition was a between-subjects factor (2 levels: HRV-Increase, HRV-Decrease). For each ANOVA, the effect of interest was a time \times condition interaction, and only data from participants with values for both time points were included. P values less than 0.05 were considered statistically significant. ANOVAs were performed with R (Version 4.0.3) and the R package 'ez'.
- Emotional well-being (all weeks):
To test whether emotional well-being changed during the course of the study and whether this depended on training condition, we fit a series of linear mixed effects models, one for each measure. For these models, fixed effects were time (1 level per week), condition (2 levels: HRV-Increase, HRV-Decrease), and a time \times condition interaction. The models included random intercepts for participants. For each model, data from all available participants at each time point was used. To assess parameter significance, F- and p-values were determined using Satterthwaite's method. P values less than 0.05 were considered statistically significant. These

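### The SAP analyses only randomised participants who completed assessments with adequate data; this post-randomisation filter discards usable pre values and leaves the arm contrast open to bias of unknown size

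*SAP*

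**What the plan says.** SAP Section 4 gives one population for the whole trial: "Population analyzed is composed by all randomization subjects who completed assessments and whose data quality was sufficient for data analysis". It does not define completion or sufficient quality. Neither document gives a motion or quality threshold, says whether quality was judged without knowledge of condition, defines an all-randomised set, or plans a missing-data analysis.

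In SAP Section 5 the primary outcome (right amygdala–mPFC connectivity) is tested by a 2 × 2 mixed ANOVA: "The effect of interest was a time \times condition interaction", and "P values less than 0.05 were considered statistically significant". That paragraph has no inclusion rule of its own, so Section 4 governs it.

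For well-being (pre/post), HRV, stress recovery, stress reactivity and the NIH Toolbox cognition tests, Section 5 states that "only data from participants with values for both time points were included". For cerebral blood flow: "Only participants with usable arterial spin labeling MRI scans at both time points were included in analyses". The weekly well-being mixed models follow a different rule: "For each model, data from all available participants at each time point was used".

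SAP Section 2 shows that exclusions were expected: "we aimed for an N=200 completion rate across the two conditions and two age groups to be able to accommodate potential exclusions for movement" and other data-quality problems.

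**The concern.** Randomisation makes the two arms comparable as allocated. A filter applied afterwards keeps them comparable only if it removes the same kind of participant from each. Here a participant who is allocated, scanned at Week 2 and then stops, or who moves too much in the Week 7 scan, leaves the primary analysis altogether, and the usable Week 2 scan goes too.

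The exercises differ by arm: slow breathing at about 6 breaths per minute against normal breathing (Protocol, Week 2). Arm-related loss is therefore possible, though no figure in the documents shows it. If loss is related to the outcome and differs by arm, the time × condition estimate is no longer the effect in the randomised groups, and its test need not hold the 5% level. Because the SAP is a draft dated 09/09/2024 and written in the past tense, an undefined quality criterion cannot be shown to predate sight of the data.

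**Working it through.** **1. The plan's own figures.** SAP Section 2 says that "a total sample size of 46 would give 90% power to detect moderate effect sizes of" f = .25, with α = .05 and a pre–post correlation of .5. For two groups and two measurements, λ = f² × N × m/(1 − ρ) = 0.0625 × 46 × 2/0.5 = 11.5, with 1 and 44 df. Power is 0.912 (0.8997 at N = 44), so 46 reproduces. For 44 per condition and d = .5, two-sided, power is 0.900, which also reproduces.

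In this convention f = .25 is an arm difference in change of √(4 × 11.5/46) = 1.0 SD.

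**2. Power is not the problem.** After 20% exclusion, power at f = .25 is above 0.99 for 193 participants (154 left), 0.998 for 121 (96 left) and 0.960 for 72 (57 left).

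**3. Size of the bias.** From the SAP: 121 + 72 = 193 participants, α = .05, ρ = .5. Numbers randomised, lost and excluded by arm are not given. Assumed:

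- no true effect and equal arms;
- a share e lost from each arm, selectively in one and at random in the other;
- those lost differ from those kept by δ SD of change.

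Then bias = e × δ. The number kept per arm is n = (N/2)(1 − e), and SE = √(2/n). The rejection rate is 1 − Φ(1.96 − bias/SE) + Φ(−1.96 − bias/SE).

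Example: N = 193, e = 0.20, δ = 1.0. n = 77.2, SE = 0.161, bias = 0.20, bias/SE = 1.24, and the rejection rate is 23.7%.

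| e | δ | bias (SD) | N = 193 | N = 121 | N = 72 |
|---|---|---|---|---|---|
| 10% | 0.5 | 0.05 | 6.3% | 5.8% | 5.5% |
| 10% | 1.0 | 0.10 | 10.1% | 8.2% | 6.9% |
| 20% | 0.5 | 0.10 | 9.5% | 7.8% | 6.7% |
| 20% | 1.0 | 0.20 | 23.7% | 16.6% | 11.8% |

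The same bias does more harm to the error rate in the larger sample. Against the 1.0 SD difference the trial was powered for, 0.05 to 0.20 SD is 5% to 20%.

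**4. Does using all available values help?** Simulation with 2 million per arm, no effect, ρ = .5, equal SDs, and random loss in the other arm. Loss in one arm depends on the stated variable plus equal noise. The all-available estimate uses the pre values of those lost, through the regression of post on pre. Bias in SD, at 10% and 20% loss:

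| Loss depends on | Completers only | All available |
|---|---|---|
| pre value | 0.07, 0.12 | about 0, about 0 |
| change | 0.14, 0.25 | 0.11, 0.20 |
| post value | 0.07, 0.12 | 0.11, 0.20 |

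The all-available analysis removes the bias when loss depends on the observed pre value. It removes only about a fifth when loss depends on change, and it is worse than completers-only when loss depends on the unseen post value.

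**The case against.** **A reader might infer that the SAP contradicts itself**, because the weekly well-being models admit everyone available. That holds only if completion in Section 4 means completing all assessments. Read per outcome, Section 4 and the weekly models coexist. The all-available rule covers one secondary analysis and does not touch the primary. It is an ambiguity to settle, and the bias point does not depend on it.

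**A reader might infer that retention was handled differently by arm.** The Protocol gives both conditions the same twice-daily practice, and it describes the completion charts and group incentive without distinguishing the arms. Only the exercise differs, and no dropout or motion figures by arm are given. This objection stands: arm-related loss is possible, not shown.

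**A reader might put the worst case higher.** Using the full-sample SE, √(4/193) = 0.144, a bias of 0.20 SD gives 28.4%. But that keeps all 193 in the SE while assuming that 20% are lost. The consistent figure is 23.7%.

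**A reader might take the mixed model as a complete cure.** Step 4 shows that it is not. The top of the range also lies outside what it repairs: under the simulation's assumptions, even losing exactly the most extreme 20% on the pre value gives a difference in change of only 0.87 SD (0.97 SD for 10%), short of 1.0.

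**Silence is not proof.** The Protocol refers to a published data paper for further detail, which may hold thresholds or exclusion counts. The SAP still needs to state them or point to them.

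**Conclusion.** The concern holds as a matter of exposure. As written, the plan conditions the primary and most pre/post contrasts on events after randomisation and discards usable pre values. It offers no all-randomised or sensitivity analysis against which to judge the result.

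Under the assumptions in step 3, bias is 0.05 to 0.20 SD. The true error rate is about 6% to 24% with 193 participants, 6% to 17% with the 121 younger adults and 5% to 12% with the 72 older adults. Both e and δ are assumed, and so is random loss in the other arm. If loss is unrelated to change, or alike in both arms, bias is near zero. It could also run against finding an effect. The documents do not support a statement that bias occurred or that the reported test missed its level. The change is worth making because the remedy needs no new data.

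**What to change.** - **Main analysis.** For the primary and the like-for-like pre/post outcomes, analyse all randomised participants, in the condition assigned, with at least one usable pre or post value. Use a likelihood-based linear mixed model (time × condition) in the R packages already used for the weekly models. Keep the both-time-points ANOVA as supportive.
- **Sensitivity analysis.** Add one that allows for missing-not-at-random, for example a delta shift applied by arm over a stated range, because the mixed model does not correct loss that depends on change or on the unseen post value.
- **Quality exclusions.** State one cut-off for both arms and apply it from files without condition labels. If it has already been applied, say whether condition was known.
- **Reporting.** Give the numbers randomised, completing and excluded, by arm and age group, with reasons. Include those with neither value, whom the mixed model cannot recover.
- **Section 4.** Define completion, and state which population each Section 5 analysis uses, including the weekly well-being models.

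The cost is SAP wording plus one extra model and one sensitivity analysis per outcome, with no new data. The main result then relies on missing-at-random. That is less demanding than the completers-only assumption but still cannot be tested from the data.
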